## **Full study protocol (Aquatic walking exercise group 2 vs. Land-based walking exercise group)**

Participants (mean age  $65 \pm 10$ ,  $n = 53$ ) were recruited with flyers, referrals, and newspaper advertisements in a metropolitan city in South Korea at multiple community health centers where the membership population was primarily female. Study allocation was determined randomly using a computerized random number generator (**Figure 1**) to the HWET group or LET group. All participants were postmenopausal females (cessation of menses for at least 12 months), sedentary, and classified as Fontaine stage II or III PAD with an ABI of 0.6 – 0.8. Sedentary lifestyle was termed as taking part in <1 hour of regular exercise per week within the previous year. Exclusion criteria included stage IV PAD (tissue loss/gangrene), previous or pending revascularization procedure, hormone replacement therapy, current smoker (smoking within the previous 6 months), psychiatric conditions, as well as pulmonary, renal, and thyroid diseases. These exclusion criteria were incorporated to avoid potential secondary disease effects on the target population examined in this study. All exercise and experimental methods were conducted in accordance with approved protocols by the Institutional Review Board. All participants provided written, informed consent and all procedures were performed in accordance with the Declaration of Helsinki. This study was registered with clinicaltrials.gov (NCT03849300).

### **Study design**

A 2-armed parallel experimental design was used (**Figure 2**). Anthropometrics, vascular function, resting metabolic rate, walking capacity, COT, and muscular strength were assessed at baseline and after the 12 weeks. All lab assessments were performed at the same time of day (8:00 AM,  $\pm 1$  h) following an overnight fast. All participants were asked to abstain from medications for at least 24 hours prior to the baseline and post-exercise therapy measurements but continued taking medications throughout the exercise therapy protocols according to their physician

instructions. After baseline measurements, participants were allocated randomly to the HWET group (n = 28) or the LBET group (n = 25). The HWET group participated in a supervised heated-water exercise therapy program for 12 weeks. The LBET group participated in supervised treadmill therapy program for the same period of time. Both exercise groups were asked to refrain from altering dietary habits throughout the study period, and researchers obtained weekly diet logs from each participant to audit caloric intake. The exercise therapy sessions and experimental measures took place at the community centers. All participants were supervised by qualified trainers during exercise therapy sessions, and measurements were taken by experienced researchers who were blinded to participant randomization.

### **Exercise programs**

The HWET group participated in a supervised heated-water exercise therapy program (**Table 1**) for 12 weeks, 4 days per week, for 60 minutes per day. The 12-week duration, exercise frequency, and intensity levels were programmed to be similar with previous water-based and land-based studies that demonstrated improvements in vascular function for older individuals and patients with PAD (3, 45, 54, 56, 87). Exercise sessions were performed in waist-to-chest-deep water (30-31°C). HR was monitored using a standard chest strap Polar HR monitor (Electro, Oy, Kempele, Finland) during each exercise session to manage the appropriate training intensity level. Intensity was programmed using heart rate reserve (HRR) and Borg's revised rating of perceived exertion scale (RPE, 0 to 10 scale). HRR was calculated as  $(\text{HRR} = [\% \text{ intensity desired} * (\text{HR}_{\text{max}} - \text{HR}_{\text{rest}})] + \text{HR}_{\text{rest}})$ . Exercise intensity was increased every 4 weeks: weeks 1-4 were at 50-60% HRR and 6-8 RPE, weeks 5-8 were at 60-70% HRR and 6-8 RPE, and weeks 9-12 were at 70-85% HRR and 6-8 RPE. Exercise sessions were monitored by qualified trainers. Chest HR monitor readings and RPE were checked every 5 minutes during the sessions. To maintain the appropriate

intensity, if the HR or RPE were too low or too high according to the exercise program, the trainer encouraged participants to increase or decrease their effort during the session. The HWET program was divided into 3 components including a warm-up, main exercise section, and a cool-down. The warm-up and cool-down included underwater stretching that emphasized major muscle groups and low-intensity gait training (forward, backward, and lateral movement) (3). The main exercises were performed for a total of 40 minutes. For the first 10 minutes of the main section, participants performed lower limb movement patterns including hip flexion-extension, hip abduction-adduction, and knee flexion-extension (3). The next 30 minutes of the main exercise session included water walking (3).

The LBET group performed a supervised walking exercise program on a treadmill. The warm-up and cool-down components included stretches similar to those in the HWET group, and the therapy program also lasted 12 weeks, 4 times per week, for 60 minutes per session (**Table 2**). The main exercise component consisted of simple movement patterns for 10 minutes that included low-intensity forward, backward, and lateral side-stepping movements on flat ground. The next 30 minutes included treadmill walking at the same intensity (HRR and RPE values) as in the HWET group. Target HRR and RPE were achieved by adjusting the treadmill speed and incline grade. Participants with leg symptoms were encouraged to exercise to near maximal leg symptoms until failure of walking.

### **Anthropometrics**

Measurements of height, total body mass, and body composition were measured before and after 12 weeks for the LBET and HWET groups. Height was measured using a standard stadiometer to the nearest 0.1 cm. Body composition was assessed using bioelectrical impedance analysis (BIA) (InBody 230, Biospace, Seoul, Korea). Total body mass (nearest 0.1 kg) and body

fat (nearest 0.1%) were recorded. Body mass index (BMI) was calculated as body mass divided by the square of height ( $\text{kg}/\text{m}^2$ ).

### **Vascular function**

With participants in the supine position, ankle-brachial index (ABI) was recorded using the VP-2000 (OMRON, Kyoto, Japan). Electrocardiogram (EKG) electrodes were placed on the forearms. BP cuffs with pulse wave sensors were wrapped around both arms (brachial artery) and ankles (posterior tibial artery). Measurements were recorded for 10-30 seconds. Brachial-to-ankle pulse-wave velocity (baPWV) was also recorded using the VP-2000 as previously described (89).

Femoral-to-ankle pulse-wave velocity (legPWV), a measurement of peripheral arterial stiffness, was measured using applanation tonometry (TU-100 and VP-2000, OMRON Healthcare, Kyoto, Japan) (56). A tonometer was placed on the femoral artery, while the pulse-wave sensor BP cuffs on the ankles and EKG electrodes remained in place from the ABI measurement. BP, EKG, and pulse waveforms were simultaneously recorded for 10-30 seconds. Data analysis was performed according to the Clinical Application of Arterial Stiffness, Task Force III (77).

Participants were then moved to a resting seated position. After 5 minutes of quiet sitting the resting HR, systolic BP, and diastolic BP were measured in duplicate using radial artery palpation and an automated sphygmomanometer (BP-200, OMRON, Kyoto, Japan), respectively, before and after 12 weeks of LBET or HWET. The average of the two measurements was recorded as the resting values. If the BP measurements differed by more than 5 mmHg, an additional measurement was taken and the two readings that were the closest (differed by  $\leq 2$  mmHg) were averaged and recorded as the resting BP (58). The interclass correlation coefficient in our laboratory for systolic and diastolic BP calculated on two measurements is  $\approx 0.97$ .

### **Resting metabolic rate**

Resting metabolic rate (RMR) was calculated using a metabolic cart (OxyCon Pro, Viasys Healthcare, Conshohocken, PA). Subjects rested in the supine position on a padded table and were asked to breathe normally and to not fall asleep during the assessment. Measurements with the metabolic cart were performed for 30 minutes.

### **Exercise tolerance and claudication assessment**

The 6-minute walk test was used to determine 6-minute walking distance, or exercise tolerance. Participants were asked to walk as many laps as possible around a 60-meter track for 6 minutes. COT was measured during the 6-minute walk test. Once the participants experienced any leg and/or foot pain during the walking test, they reported the pain to the trainers.

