### **Statistical analysis plan**

The Shapiro-Wilk test was used to assess normality of the data. Independent *t* tests were used to determine any baseline differences between the LBET and HWET groups. A two-way repeated measure analysis of variance (ANOVA) [group (LBET and HWET) x time (pre- and post-12 weeks)] was used to assess changes between pre- and post- LBET vs. HWET within and between groups on the dependent variables. When a significant interaction was found, paired *t* tests were used for post-hoc comparisons. All analyses were performed using SPSS 24 (SPSS Inc. Chicago, IL, USA). Statistical significance was set to  $p < 0.05$ . Data are presented as Mean  $\pm$  SD. A power analysis calculation was used to determine the minimum sample size of 50 (25 in each group) would allow for the observation of a change of 3-5% between groups (LBET vs. HWET) for legPWV with a power of 90% (4, 54).

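### Aquatic group 2 vs. land-based comparison: COT has no unit and no score for a pain-free 6-minute walk; if such walks are left blank, the two-visit ANOVA drops those participants and loses some power

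*Combined protocol and SAP*

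**What the plan says.** All references are to the second protocol in the file (aquatic group 2, labelled HWET, against land-based walking, labelled LBET).

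- Study design lists COT among the outcomes: "walking capacity, COT, and muscular strength were assessed at baseline and after the 12 weeks". The abbreviation is not expanded there or elsewhere.
- Exercise tolerance and claudication assessment sets the observation window: "Participants were asked to walk as many laps as possible around a 60-meter track for 6 minutes". It then says "COT was measured during the 6-minute walk test" and adds one operational detail: "Once the participants experienced any leg and/or foot pain during the walking test, they reported the pain to the trainers".
- The participants paragraph describes the population as "classified as Fontaine stage II or III PAD with an ABI of" 0.6 to 0.8.
- Statistical analysis plan gives one model for all outcomes: "A two-way repeated measure analysis of variance (ANOVA) [group (LBET and HWET) x time (pre- and post-12 weeks)] was used", applied "within and between groups on the dependent variables". The follow-up is conditional: "When a significant interaction was found, paired" *t* tests are used. It has no separate method for COT and no rule for missing or censored values.

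**The concern.** The section heading and the pain report suggest that COT is the time to first leg or foot pain. Observation stops at 6 minutes, so a participant who finishes without pain has no onset to record. The plan does not say whether that person gets 360 s, another value or a blank.

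The choice matters because the planned ANOVA and the paired tests use only participants with a number at both visits. Under a blank, missingness depends on the outcome itself. People pain-free at week 12 have the longest pain-free walking, and people pain-free at baseline are the least symptomatic. If one arm does better at week 12, more of that arm's best results are removed. With 28 and 25 participants there is little room to lose any.

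**Working it through.** **Inputs from the documents.** Arms of 28 and 25 (Study design); a window of 6 × 60 = 360 s; significance level 0.05 (taken as two-sided). The plan gives no power figure for COT to reproduce: its sample size rests on legPWV.

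**Assumed inputs, not in the documents.** COT is a time in seconds. Onset is log-normal with log-SD 0.6, and the pre-post correlation on the log scale is 0.6. Both arms have the same baseline median, and one arm has a longer median at week 12. The medians are chosen to span low and high pain-free shares.

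**Step 1: pain-free share.** The share is 1 − Φ(ln(360/median)/0.6). For a week-12 median of 180 s this is 1 − Φ(0.693/0.6) = 1 − Φ(1.155) = 12.4%. Medians of 130 and 150 s give 4.5% and 7.2%; medians of 240, 300 and 360 s give 25.0%, 38.1% and 50%.

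**Step 2: the planned test.** With two visits, the group-by-time F test is the two-sample *t* test on change (week 12 minus baseline). It was simulated in two ways: with every value capped at 360 s and everyone kept, and after removing anyone at or above 360 s at either visit. There were 20,000 trials per scenario (Monte Carlo SE at most 0.4 points).

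| Baseline; week-12 medians (s) | Pain-free, better arm | Lost of 53 | Difference in change, 360 s entered → excluded (s) | Power, 360 s entered → excluded | Loss (points) |
|---|---|---|---|---|---|
| 100; 130 vs 100 | 5% | 2.3 | 33 → 29 | 38% → 35% | 3 |
| 110; 150 vs 110 | 7% | 3.4 | 41 → 36 | 51% → 45% | 6 |
| 120; 180 vs 130 | 12% | 5.5 | 47 → 40 | 55% → 46% | 9 |
| 150; 240 vs 180 | 25% | 11.6 | 44 → 37 | 44% → 32% | 12 |
| 165; 300 vs 210 | 38% | 16.8 | 53 → 46 | 57% → 38% | 19 |
| 180; 360 vs 240 | 50% | 21.7 | 56 → 51 | 61% → 39% | 22 |

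A repeat with separate code agreed to within about one point of power.

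**Step 3: sensitivity.** Over 30 settings (log-SD 0.4 to 0.8, correlation 0.4 to 0.8), exclusion had lower power in all 30: by 1 to 10 points in the low-share settings and 8 to 23 in the high-share ones. The estimated difference was smaller in 29 of 30. A separate set with log-SD 0.5 and baseline medians of 120 to 240 s also showed lower power after exclusion in all nine scenarios, with a smaller difference in seven. At log-SD 0.4 and baseline medians of 80 to 100 s, 0.0 to 0.2 people are lost and the cost is under 1 point.

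**Step 4: false positives.** With both arms at the same week-12 median (115, 150, 210 or 300 s), rejection was 4.9 to 5.1% after exclusion and 5.0 to 5.1% with 360 s entered.

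**Step 5: a limit on the direction.** With equal week-12 medians of 240 s but log-SD 0.8 in one arm and 0.4 in the other, the curves cross. A within-test difference of about −8 s becomes about −32 s after exclusion, and rejection rises from 6% to 23%. The 23% moves between 18 and 32% as the assumed baseline changes.

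**Step 6: ANCOVA.** Week-12 COT capped at 360 s was regressed on arm and capped baseline COT, with a baseline pain-free indicator where any occurred. With everyone kept, power in the six rows is 43/56/60% and 50/66/74%. Against the capped planned test that is a gain of 5/5/5 and 6/9/13 points (4 to 13 across repeat runs). ANCOVA after exclusion gives 39/49/48% and 32/37/35%, so baseline adjustment alone does not repair exclusion.

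**The case against.** The strongest reply is that exclusion is an inference. A reader might infer that the planned ANOVA does exclude pain-free participants. The documents do not say so: the model only needs a number at both visits, and staff may have entered 360 s, in which case nobody is lost. This stands. What the text shows is a missing scoring rule, and the power loss is conditional on a blank.

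A reader might also infer that power is lost whenever one arm has longer onset at both visits. It does not follow for the group-by-time test. With one arm 1.6 times longer at both visits and no difference in training effect, there is no interaction to detect, and the test rejects at about 5% under either handling. The loss belongs to the case where the arms diverge at week 12.

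Third, the pain-free share may be small. The population is Fontaine II or III with reduced ABI, and any leg or foot pain counts, which is a low threshold. This is fair, and it is why the low-share rows should lead. It does not make the share zero: the exercise programme section refers to participants with leg symptoms as a subset, and both arms are trained for 12 weeks.

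Fourth, COT does not drive the sample size, and in these scenarios its power is only 38 to 61% even when scored properly. Both points hold and limit the severity.

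Finally, entering 360 s within the planned ANOVA would already remove the exclusion. That is correct: the ANCOVA is a separate gain in efficiency.

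**Conclusion.** The concern holds in conditional form. The plan gives COT no unit and no score for a pain-free walk, although a 6-minute ceiling is built into the measurement. If such walks are blank, the planned analysis removes participants because of their outcome. When one arm's onset is longer at week 12, this costs about 3 to 9 points of power at an assumed 5 to 12% pain-free in the better arm, and less below that. It shrinks the estimated difference in most settings, though not all. The 12 to 22 point losses are shown for range only, since nothing in the documents supports shares of 25 to 50%.

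The documents do not support a reading that false positives are inflated when the arms share a distribution, nor that the bias always runs towards no difference, as the crossing-curve case shows. The legPWV analysis and the stated sample size are unaffected. Every size quoted rests on assumed medians, spread and correlation. Severity is at the low end and confidence is medium.

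**What to change.** In Exercise tolerance and claudication assessment (second protocol): expand COT, state its unit and when timing starts, and record a walk finished without pain as 360 s with a flag, not as missing.

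In the second Statistical analysis plan: keep every tested participant, and analyse week-12 COT, capped at 360 s, by ANCOVA with arm and baseline COT. A baseline pain-free indicator is optional, as is a Tobit or Cox model as a sensitivity analysis. Label the result as mean pain-free walking time within 6 minutes, and report pain-free counts by arm and visit.

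The cost is wording in two sections and one standard model, with no new measurements. It does require that pain-free tests can be identified. The plan does not say they were logged, but a recorded 6-minute distance with no COT value may show them. The downside is that the estimate says nothing about onset beyond 6 minutes.

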### **Cardiorespiratory capacity and 6-minute walking distance**

The Cornell modified Bruce treadmill test was used to determine the maximal volume of  $O_2$  consumption ( $VO_{2max}$ ) (32). This Bruce protocol modification has been proven to be valid and reproducible (48) and has been used in disease populations (76). The modified Bruce consists of 11, 2-minute stages that progress from 1.7 mph and 0% grade to 5 mph and 18% grade (48). The treadmill test was ended when the participants reached volitional fatigue. Expired gases were measured with a metabolic cart (OxyCon Pro, Viasys Healthcare, Conshohocken, PA).

The 6-minute walk test was used to determine maximal walking distance, or exercise tolerance. Participants were asked to walk as many laps as possible around a 100-meter track for 6 minutes.

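### In the second study COT is timed in a self-paced walk and analysed without regard to pace, so a change in COT cannot be separated from a change in walking speed

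*Combined protocol and SAP*

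**What the plan says.** The point concerns the second study in the combined document, which compares heated-water exercise (HWET) with land-based exercise (LBET).

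- **Test.** Under *Exercise tolerance and claudication assessment*: "Participants were asked to walk as many laps as possible around a 60-meter track for 6 minutes". The same section adds that "COT was measured during the 6-minute walk test". It states no speed, grade or pacing rule.
- **Event.** "Once the participants experienced any leg and/or foot pain during the walking test, they reported the pain to the trainers". Nothing is said about noting where on the track this happened.
- **Outcome.** *Study design* lists it among the pre/post measures: "walking capacity, COT, and muscular strength were assessed at baseline and after the 12 weeks".
- **Analysis.** The second *Statistical analysis plan* applies one model to every outcome, a two-way repeated-measures ANOVA (group by time), which "was used to assess changes between pre- and post- LBET vs. HWET within and between groups on the dependent variables". Pace does not enter it.
- **Training.** Under *Exercise programs*, both arms do 30 minutes of walking per session at the same heart-rate-reserve and exertion targets, one arm in water and the other on a treadmill. For the treadmill arm, "Target HRR and RPE were achieved by adjusting the treadmill speed and incline grade".

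The only test with a set workload is the treadmill test of the first study: "The modified Bruce consists of 11, 2-minute stages that progress from 1.7 mph and 0% grade to 5 mph and 18% grade". The second study describes no such test.

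The available text does not expand COT. The section title and the pain-report sentence make claudication onset time the natural reading, and it is used here.

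**The concern.** Time to first pain shows how well a patient tolerates walking when the workload is the same at both visits. Here the participant chooses the workload, under an instruction that rewards speed, after 12 weeks of a walking programme that may change speed. Someone who reaches pain at the same point on the track but gets there faster is recorded with a shorter COT. Someone who walks more slowly is recorded with a longer one. In neither case need the claudication threshold have moved.

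What is at stake is the reading of the claudication result in participants with Fontaine stage II or III disease. A real gain could appear as no change or a loss, and a slower walk could appear as a gain. Randomisation does not remove this, because pace at week 12 can itself be affected by the assigned training.

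**Working it through.** **Plan's own figure.** The plan gives no figure for COT. Its only sample-size statement (50 participants, 25 per group, 90% power) rests on legPWV, so there is nothing to reproduce for this point.

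**Inputs from the documents.** Walk of 6 minutes (360 s) on a 60-metre track; visits at baseline and 12 weeks.

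**Inputs assumed.** All onset distances, speeds and gains below. The documents give none.

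**Step 1: the relation.** Let D be the distance to first pain and v the mean speed up to first pain. Then COT = D / v. If D changes by a fraction g and v by a fraction s between visits,

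COT change = (1 + g) / (1 + s) − 1.

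**Step 2: values.**

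| Onset distance (g) | Speed to onset (s) | COT change |
|---|---|---|
| 0 | +5% | 1/1.05 − 1 = −4.8% |
| 0 | +10% | 1/1.10 − 1 = −9.1% |
| 0 | +15% | 1/1.15 − 1 = −13.0% |
| +5% | +10% | 1.05/1.10 − 1 = −4.5% |
| +10% | +10% | 1.10/1.10 − 1 = 0 |
| +15% | +10% | 1.15/1.10 − 1 = +4.5% |
| 0 | −10% | 1/0.90 − 1 = +11.1% |

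In seconds: pain at 150 m comes at 150 s when walking at 1.0 m/s and at 150/1.1 = 136 s at 1.1 m/s. COT rises only when onset distance grows by a larger proportion than speed. The last row shows the ambiguity in the favourable direction.

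**Step 3: between arms.** Suppose onset distance is unchanged in both arms. If both speed up by 10%, both show −9.1% and the comparison of relative change is undisturbed. If one speeds up by 5% and the other by 10%, they show −4.8% and −9.1%, a gap of 4.3 percentage points against the faster arm. Which arm that would be, if either, cannot be read from the documents.

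**Step 4: the same test applied to onset distance.** Step 2 takes distance as the stable quantity. If pain instead began at a fixed time T, then D = v × T, and walking 10% faster would raise onset distance by 10% with COT unchanged. Onset distance is therefore also pace-dependent. Distance, time and speed to onset are needed together.

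**Step 5: what six-minute distance can supply.** Mean speed over the whole walk is 6MWD / 360, so approximate onset distance is COT × 6MWD / 360. This is exact only if speed before pain equals the six-minute mean. Assume 1.0 m/s up to pain at 180 s, then 0.8 m/s for the other 180 s. Then 6MWD = 180 + 144 = 324 m, and the approximation gives 180 × 324/360 = 162 m against a true 180 m, 10% too low. It is usable as a labelled sensitivity analysis, not as a measurement.

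**The case against.** The strongest reply is that the percentages are an identity with chosen inputs and are not evidence. That is right: the documents support the statement that COT can move with pace, not that it did. Four further objections deserve an answer.

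- **Direction of bias.** Because only the land arm trains on a treadmill with adjustable speed, a reader might infer that COT is biased against that arm and towards HWET. The documents do not support this. Both arms train walking at the same intensity targets, and the treadmill target can be met through incline as well as speed. The land arm's encouragement to walk on to near-maximal symptoms could also alter pain reporting in an unknown direction.
- **COT and 6MWD as opposites.** A reader might infer that the two outcomes must pull against each other. That needs an unchanged onset distance and a walk without slowing or stopping. In the Step 5 example, let pain start at 240 s rather than 180 s at the same two speeds: 6MWD becomes 240 + 0.8 × 120 = 336 m against 324 m, and both outcomes rise.
- **Replacing COT.** A reader might conclude that onset distance should take COT's place, or that a shorter COT should be disregarded when speed rose. Step 4 rules out the first. The second would discount unfavourable results only.
- **Reach and timing.** COT does not drive the sample size, and the text describes enrolment and testing in the past tense, so unrecorded positions may be beyond recovery. Both points stand. They limit the severity and call for a fallback, but the result still needs interpreting.

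It can also be said that 6MWD from the same walk already reveals pace. It gives the six-minute mean, not the speed before pain, and the plan does not say it will be used to interpret COT.

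**Conclusion.** The point holds as a matter of interpretation. In the second study COT mixes the claudication threshold with walking pace, in either direction, and neither the test description nor the analysis plan provides a way to separate them. For illustration, a 10% change in pace at unchanged onset distance moves COT by −9.1% (faster) or +11.1% (slower), and a 5% gain in onset distance with 10% faster walking appears as −4.5%. These sizes rest on assumed gains.

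The conclusion rests on two inferences: that COT means claudication onset time, and that participants chose their own pace, since no pace is stated. Any distortion of the arm comparison requires pace changes that differ between arms, and its direction is not established. The legPWV power statement is unaffected. This should be addressed, but it does not threaten the study as a whole.

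**What to change.** 1. In *Exercise tolerance and claudication assessment* (second study), spell out COT. At first pain, record the position on the 60-metre track (laps completed plus metres) as well as the time.
2. In the second *Statistical analysis plan*, analyse claudication onset distance alongside COT with the same group-by-time model, and report mean speed to onset by arm and visit. State that a COT change in either direction will be interpreted only together with onset distance and speed to onset.
3. If the walks are complete and position was not recorded, report COT beside 6MWD by arm and visit. Add approximate onset distance (COT × 6MWD / 360 s) for participants who reported pain, as a labelled sensitivity analysis, noting that slowing after pain makes it too short.

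**Cost.** For future walks, one more entry on the test sheet and a few sentences in the plan, with no extra test or staff. For completed walks, only a further table and a caveat. The small downside is that onset distance also depends on pace, so it supplements COT and does not replace it.
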